13.3 Stratification Factors

There will be no stratification of patients on this study.

13.4 Interim Monitoring Plan

Data safety and monitoring will be performed per DFCI guidelines. We first note that veneteoclax and obinutuzumab (K. Fischer et al., 2019; Fischer et al., 2017), acalabrutinib and obinutuzumab (Woyach, Awan, et al., 2017; Woyach et al., 2020), and venetoclax plus ibrutinib (a related BTK inhibitor) (Tam et al., 2018) combination therapy has been tested in patients without any concerning safety signals so far. If in the first 10 patients who receive at least one cycle of triple therapy with acalabrutinib, venetoclax, and obinutuzumab, 3 or more patients develop unexpected toxicity, this will trigger a consultation with the DSMC about whether to stop accrual. Unexpected toxicities would include the following events that occur during the first cycle of triple therapy, unless they are clearly due to extraneous causes: grade 4 or higher infusion reaction, grade 4 or higher infection, grade 4 or higher neutropenia, any cases of clinical

TLS, or other grade 3 or higher, clinically significant nonhematologic toxicity related to study treatment, except asymptomatic laboratory abnormalities or nausea/vomiting/diarrhea that improves with supportive care. With this design, the probability of triggering a consultation is 0.07 if the true but unknown rate of grade 3 or higher treatment related toxicity is 10%, 0.18 if the rate is 15%, 0.74 if the rate is 35%, and 0.83 if the rate is 40%.

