2.4 Rationale for Study Expansion

Preliminary Safety Data

As of 1/1/2019, 25 patients have enrolled, with no screen failures. Twelve patients have reached the portion of the study where they take all three drugs in combination, and no unanticipated safety signals have been seen. The most frequent adverse events reported to date have been hematologic in nature, as is expected in the CLL patient population. We have seen a lower than expected rate of hospital admissions for TLS monitoring in patients initiating venetoclax, with only 1 patient requiring hospital admission due to persistent disease bulk at time of venetoclax initiation. This demonstrates that acalabrutinib and obinutuzumab therapy can successfully debulk the disease and decrease the risk of TLS with venetoclax initiation. One patient did experience laboratory TLS during cycle 2 with initial obinuzutumab administration, but this was prior to venetoclax initiation and resolved without clincial sequelae. No patients have discontinued study therapy due to toxicity.

Preliminary Efficacy Data

Twelve participants have reached cycle 4 day 1, when the initial disease re-staging occurs with CT scans and an optional bone marrow biopsy. Of the 12 patients who have reached this time point, 10 (83%) have already achieved a partial response by CT criteria; the remaining 2 patients had a 36% and 49% reduction in nodal burden, just missing the required 50% cut-off to achieve a partial response and thus being classified as stable disease. No patients have disease progression to date.

TP53-Aberrant Disease Is an Unmet Need

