Given the favorable safety profile, preliminary demonstration of efficacy, and rapid accrual of the study so far, we are expanding the study to provide additional power to more confidently report the primary outcome for the subgroup with *TP53*-abberant disease, the group most likely to benefit from this combination novel agent approach. Greater patient numbers will also allow for more robust analysis of the secondary endpoints including prespecified subgroup analyses, and to increase the number of samples available to perform the exploratory and correlative objectives.

Additionally, we plan to turn this into a multicenter study to allow our Dana-Farber Cancer Care Collaborative sites to participate. These are community sites closely tied to Dana-Farber but a different patient population from our main campus. The logistics of opening and monitoring these sites are more straightforward than for external sites, and by including these patients, we can demonstrate the feasibility of administering the AVO regimen outside of major academic medical centers.

2.5 Rationale for Modifying Treatment Discontinuation Parameters at Cycle 24

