13.2 Sample Size, Accrual Rate and Study Duration

This is a one-stage study to determine the MRD-negative CR/CRi rate in the bone marrow after 15 cycles of AVO combination therapy. In a previous study of venetoclax plus rituximab in the relapsed/refractory population, the CR/CRi rate was 51%, and 80% of these responses were bone-marrow MRD-negative, for an MRD-negative CR/CRi rate of 41% (Seymour et al., 2017). Furthermore, 21 out of 25 CRs in this study occurred after 18 months of therapy, thus we will assume that ~80% of all marrow MRD-negative CRs will have occurred after 15 months of therapy here, leading to an expected marrow MRD-negative CR/CRi rate of 33%. Of note, this study was done in a relapsed/refractory population. Given that the depth of response is likely to be greater in the frontline setting, we are using an MRD-negative CR/CRi rate of 40% as the null hypothesis. With the addition of acalabrutinib, we hypothesize that the MRD-negative CR/CRi rate will be 60% or higher (alternative hypothesis). Initially, we planned to enroll 37 patients, and assuming approximately 1 screening failure this meant that 36 patients would be evaluable for the primary endpoint. This cohort has now completed enrollment and is referred to as cohort 1. We will now expand the study to include a second cohort of 35 patients with high-risk disease, defined as 17p deletion and/or TP53 mutation (cohort 2). In cohort 2, we will have 80% power and one-sided type I error of 0.07 for an exact one-sample binomial test comparing an expected 55% response rate to the assumed 35% response rate for standard-of-care treatment in this high risk group. A patient will be considered unevaluable for response and replaced if the patient decides to withdraw from the study prior to the administration of the first dose of study drug. Based on the accrual rate of the study to date of 3 patients per month, we anticipate that accrual

of this study will complete within approximately 12 months from activation of cohort 2. Up to an additional 15 months of follow-up will be required on the last participant accrued to observe participant response after the 15th cycle of protocol therapy, for a total study duration of approximately 2.5 years. Evaluation of secondary endpoints, such as 3 year overall survival, will take up to three years after enrollment of the final subject.

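### The only numeric toxicity trigger is used up by cohort 1, and its wording can leave out patients whose toxicity ends the triplet early; restart it for cohort 2 and count every starter

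*Combined protocol and SAP*

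**What the plan says.** Section 13.4 defines the patients watched by the trigger: "If in the first 10 patients who receive at least one cycle of triple therapy". The threshold and the action follow: "3 or more patients develop unexpected toxicity, this will trigger a consultation with the DSMC about whether to stop accrual". Counted events are limited to "events that occur during the first cycle of triple therapy, unless they are clearly due to extraneous causes". The list covers infusion reaction, infection and neutropenia at grade 4 or above, any clinical tumor lysis syndrome (TLS), and most other clinically significant, treatment-related non-hematologic toxicity at grade 3 or above. The stated operating characteristics are "the probability of triggering a consultation is 0.07 if the true but unknown rate of grade 3 or higher treatment related toxicity is 10" percent, then "0.18 if the rate is 15%, 0.74 if the rate is 35%, and 0.83 if the rate is 40" percent.

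Section 2.4 gives the position on 1 January 2019: 25 patients enrolled, none off therapy for toxicity, and "Twelve patients have reached the portion of the study where they take all three drugs in combination". On the expansion, the same section says "we plan to turn this into a multicenter study", bringing in community sites. Section 13.2 says of the first cohort (37 planned): "This cohort has now completed enrollment and is referred to as cohort 1". It then adds 35 patients with 17p deletion or *TP53* mutation.

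Sections 11.1 and 13.7 make everyone who receives any study treatment evaluable for toxicity. Section 12.2 provides for DSMC review up to four times a year, or more often if needed, without a numeric boundary. The synopsis also defines unexpected toxicities but attaches no count to them.

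**The concern.** There are two separate weaknesses.

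1. **Scope.** The trigger applies to the first ten triplet patients only, and nothing in the documents restarts or extends it. The expansion changes both the population (*TP53*-aberrant only) and the setting (community sites), but the one pre-specified count belongs to cohort 1.

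2. **Denominator.** Events are counted during the first triplet cycle, but only in patients who receive at least one such cycle. Some listed events end or interrupt a triplet drug under the protocol's own rules. A grade 4 infusion reaction ends obinutuzumab (sections 5.3 and 6.2). Grade 4 non-hematologic toxicity ends venetoclax unless attributed elsewhere (section 6.1, Table 7). A patient with such an event early in the cycle, or who dies in it, may never have received one cycle and so would not be among the ten.

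At stake is whether the sponsor's own early check works in the new cohort, and whether its stated sensitivity applies to all patients who start the triplet or only to those who get through a cycle.

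**Working it through.** **Inputs.** From section 13.4: n = 10, threshold 3, true rates 10%, 15%, 35% and 40%. From section 2.4: 12 patients at the triplet by 1 January 2019. From section 13.2: cohort 1 enrollment complete, cohort 2 of 35, total accrual 71. Not in the documents: f, the share of patients with a counted event who do not receive a full first triplet cycle. I take 10%, 25% and 50% as an assumed range.

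**Step 1: reproduce the plan's figures.** Let X be the number of the ten with a listed event, and p the probability of one:

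P(X ≥ 3) = 1 − [(1−p)^10 + 10p(1−p)^9 + 45p²(1−p)^8]

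| p | Stated | Computed |
|---|---|---|
| 0.10 | 0.07 | 0.0702 |
| 0.15 | 0.18 | 0.1798 |
| 0.35 | 0.74 | 0.7384 |
| 0.40 | 0.83 | 0.8327 |

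All four agree to two decimals. They require each of the ten to carry the full rate p, so they hold for all starters only if no affected starter is left out.

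**Step 2: who is covered.** Twelve patients had reached the triplet by 1 January 2019. That does not show that ten had finished a cycle by that date. Cohort 1 has since completed enrollment, with 37 planned, so cohort 1 supplies the first ten under either reading of the denominator. Coverage is 10 of 71 patients (14%) overall and 0 of 35 in cohort 2.

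**Step 3: effect of leaving out early stoppers.** Of N starters, pN have an event and fpN of those are left out. The remaining N(1 − pf) patients include p(1−f)N with an event, so the event rate among counted patients is q = p(1−f)/(1−pf). Putting q into the Step 1 formula gives:

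| p | f | q | P(X ≥ 3) |
|---|---|---|---|
| 0.35 | 0 | 0.350 | 0.738 |
| 0.35 | 0.10 | 0.315/0.965 = 0.326 | 0.684 |
| 0.35 | 0.25 | 0.2625/0.9125 = 0.288 | 0.584 |
| 0.35 | 0.50 | 0.175/0.825 = 0.212 | 0.359 |
| 0.40 | 0 | 0.400 | 0.833 |
| 0.40 | 0.10 | 0.36/0.96 = 0.375 | 0.789 |
| 0.40 | 0.25 | 0.30/0.90 = 0.333 | 0.701 |
| 0.40 | 0.50 | 0.20/0.80 = 0.250 | 0.474 |

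**Step 4: the trigger restarted for cohort 2, all starters counted.** The probabilities are those of Step 1: 0.070, 0.180, 0.738 and 0.833. At intermediate rates they are 0.322 (p = 0.20) and 0.474 (p = 0.25).

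**Step 5: timing.** At the 3 patients a month in section 13.2, the tenth cohort 2 patient enrolls at about 10/3 = 3.3 months. Four 28-day cycles are 112 days, about 3.7 months, so that patient ends cycle 4 at about 7 months. By then about 7 × 3 = 21 of 35 are enrolled and 14 are still to come. A third event could trigger the consultation sooner.

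**The case against.** A first-ten check on a new triplet is meant to be used once. Cohort 2 receives the same drugs on the same schedule, and section 2.4 reports no unanticipated safety signal, so not repeating the check is a defensible design choice. It remains a choice the plan does not explain for the new population and sites.

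A reader might infer that cohort 2 has no safety monitoring or no early warning. The documents do not support that. DSMC meetings can be more frequent if required (section 12.2), grade 5 events are reported within one business day whatever the attribution (section 7.4), and life-threatening toxicity goes to the sponsor immediately (Appendix J). A single fatal event would be seen without waiting for a third case. What is missing is a pre-specified count.

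A reader might also infer that toxicity in cohort 1 was missed. Section 2.4 does not support that either, as nobody had stopped for toxicity by 1 January 2019. The phrase about receiving a cycle can also be read as starting one. Events of grade 4 or higher include deaths, which suggests that the authors meant to count them. That reading is plausible, but the text does not settle it.

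The larger values of f have no documentary support. Grade 4 neutropenia, a likely contributor, leads at first occurrence to a hold and then resumption (section 6.1, Table 8), so f could be small. At f = 10% the loss is only 0.74 to 0.68.

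Finally, a restarted 3-of-10 trigger covers only ten of the 35 and does not guarantee that any of the ten comes from a community site. That objection stands.

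**Conclusion.** The point holds as one of scope and wording. The arithmetic in section 13.4 is correct. No numeric toxicity trigger operates for the 35 cohort 2 patients; general DSMC review and expedited reporting do.

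The denominator is narrower, on a literal reading, than the toxicity population in sections 11.1 and 13.7, and the printed probabilities do not allow for that. The size of this second effect is unknown. At a true rate of 35%, the trigger probability would be 0.68, 0.58 or 0.36 instead of 0.74 if 10%, 25% or 50% of affected patients were left out. Those shares are assumptions, and the effect may have been nil in the first ten. The trigger prompts a consultation and stops nothing by itself, so this is an inexpensive improvement worth making. It is not a failure of safety oversight.

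**What to change.** Add to section 13.4, for example: *The trigger is applied again in cohort 2. If 3 or more of the first 10 cohort 2 patients who start triple therapy have a listed event in their first triplet cycle, the DSMC is asked whether accrual should stop. Every patient who starts counts, whether or not the cycle is completed.* Define the start as the first day on which all three drugs are in use. Keep the existing event list and first-triplet-cycle window. The printed probabilities then apply to everyone who starts the triplet.

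The cost is one paragraph, and the data are already collected. The downside is an unneeded consultation with probability 0.07 to 0.18 at true event rates of 10-15%, and 0.32 to 0.47 at 20-25%. The higher rates are possible because grade 4 neutropenia counts: section 7.1 cites grade 3 or 4 neutropenia in 40-50% of venetoclax patients, without giving the grade 4 share or the first-cycle share. The other 25 cohort 2 patients would remain under general DSMC review, and the section should say so.

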Acalabrutinib will be administered orally twice daily during each 28-day cycle. Obintuzumab will be given intravenously at the standard dosing of six monthly cycles (with loading doses administered weekly during the first month). Venetoclax will be given orally daily with ramp-up stepwise dosing during the first month of therapy until the standard dose is achieved. After the six cycles of obinutuzumab are completed, venetoclax and acalabrutinib will continue as combination therapy until cycles 15, 24, or indefinitely (as outlined in Study Overview, above).

Definition of Unexpected Toxicities

Unexpected toxicities would include the following events that occur during AVO treatment, unless they are clearly due to extraneous causes: any grade 3 or higher clinically significant nonhematologic toxicities related to study treatment, grade 4 or higher infusion reaction, grade 4 or higher tumor lysis syndrome, grade 4 or higher infection, and grade 4 or higher neutropenia. Grade 3 or 4 drug-related toxicities occurring after the first cycle of treatment will be discussed with the Principal Investigator and will be considered in decisions regarding the recommended dose for future studies. The IWCLL Grading Scale for Hematologic Toxicity in CLL Studies will be used to grade hematologic toxicities and the National Cancer Institute Common Terminology Criteria for Adverse Events (NCI-CTCAE) Version 5.0 will be used to grade non-hematologic toxicities during the trial unless otherwise specified.

Study Drug

Acalabrutinib is administered orally twice daily as a tablet formulation. The acalabrutinib drug product is supplied as 100mg tablets. Obinutuzumab is administered intravenously. Venetoclax is administered orally daily as a tablet formulation, with tablet strengths varying based on dosing.

Key Eligibility Criteria (for complete eligibility criteria, see section 3.1)

Inclusion Criteria

- Subjects must have CLL, SLL, or B-prolymphocytic leukemia (B-PLL)
- Subjects must have *TP53*-aberrant disease, defined as the detection of del(17p) and/or the presence of a *TP53* mutation
- Participants must have measurable disease (lymphocytosis > 5,000 / μ l, or palpable or CT measurable lymphadenopathy \geq 1.5 cm, or bone marrow involvement \geq 30%).

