7.1 Expected Toxicities

Adverse Events Lists

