Obinutuzumab can cause severe and life-threatening IRRs; 65% of patients with CLL experienced a reaction to the first 1000 mg infused of obinutuzumab, and 38% of iNHL patients experienced a reaction on Day 1 of obinutuzumab infusion. IRRs within 24 hours of receiving obinutuzumab have occurred. IRRs can also occur with subsequent infusions. Symptoms may include hypotension, tachycardia, dyspnea, and respiratory symptoms (e.g., bronchospasm, larynx and throat irritation, wheezing, and laryngeal edema). Most frequently reported symptoms include nausea, fatigue, dizziness, vomiting, diarrhea, hypertension, flushing, headache, pyrexia, and chills. Management of IRRs is discussed in section 5.3.1.

Tumor Lysis Syndrome

TLS, including fatal cases, has been reported in patients receiving obinutuzumab. Patients with high tumor burden, high circulating lymphocyte count (> 25×10^9 /L) or renal impairment are at greater risk for TLS and should receive appropriate tumor lysis prophylaxis with antihyperuricemics (e.g., allopurinol or rasburicase) and hydration prior to the infusion of obinutuzumab. Continue prophylaxis prior to each subsequent obinutuzumab infusion, as needed. The laboratory parameters (including electrolytes and renal function) of patients considered at risk for TLS can be monitored as needed for patients at greater risk of TLS.

Infections

Serious bacterial, fungal, and new or reactivated viral infections can occur during and following the completion of obinutuzumab therapy. Fatal infections have been reported. Obinutuzumab should not be administered to patients with an active infection. Patients with a history of recurring or chronic infections may be at increased risk of infection.

Neutropenia

Severe and life-threatening neutropenia, including febrile neutropenia, has been reported during

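### Do the differing uses of the term unexpected toxicity in the synopsis, section 13.4 and section 7 weaken the safety trigger or adverse event reporting?

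*Combined protocol and SAP*

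**What the plan says.** Section 13.4 sets one rule. If 3 or more of the first 10 patients who receive at least one cycle of triple therapy have an unexpected toxicity, the DSMC is consulted about stopping accrual. The definition follows at once: "Unexpected toxicities would include the following events that occur during the first cycle of triple therapy, unless they are clearly due to extraneous causes". It lists grade 4 or higher infusion reaction, infection and neutropenia, and any clinical "TLS, or other grade 3 or higher, clinically significant nonhematologic toxicity related to study treatment, except asymptomatic laboratory abnormalities" and gastrointestinal symptoms that improve with supportive care. The probability of a consultation is then given as "0.07 if the true but unknown rate of grade 3 or higher treatment related toxicity is 10" per cent, with 0.18, 0.74 and 0.83 at 15%, 35% and 40%.

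The synopsis has its own definition: "Unexpected toxicities would include the following events that occur during AVO treatment, unless they are clearly due to extraneous causes". It covers clinically significant, treatment-related non-hematologic toxicity of grade 3 or higher, plus "grade 4 or higher infusion reaction, grade 4 or higher tumor lysis syndrome, grade 4 or higher infection, and grade 4 or higher neutropenia".

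Section "7.1 Expected Toxicities" describes the same four kinds of event as known risks, at severe, life-threatening or fatal level. Two examples are "Obinutuzumab can cause severe and life-threatening IRRs" and, of infections, "Fatal infections have been reported". Section 7.3 separately defines an unexpected adverse event as one not listed in the prescribing information or investigator's brochure.

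**The concern.** One term appears to carry three meanings. A grade 2 clinical tumor lysis syndrome in the first triple cycle counts under 13.4 but not under the synopsis. A grade 4 neutropenia in cycle 8 counts under the synopsis but not under 13.4. Under 7.1 both belong to recognized risks.

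The word also has consequences elsewhere. In the DF/HCC table in section 7.4, a grade 4 event is reportable within 10 calendar days if unexpected and needs no expedited report if expected. Section 12.2 lists unexpected adverse events among the information the DSMC may receive. If sites took expectedness from different pages, the same event could be handled differently, and cohort 2 (35 patients) could be monitored on an unclear basis.

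Finally, the probabilities in 13.4 are tied to the rate of treatment-related toxicity of grade 3 or higher, which is not exactly what the rule counts.

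**Working it through.** **1. The stated probabilities.** Inputs from 13.4: n = 10 and a trigger at 3 or more. With X ~ Binomial(10, p),

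P(X ≥ 3) = 1 − [(1−p)^10 + 10·p·(1−p)^9 + 45·p²·(1−p)^8].

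| p | Bracketed sum | P(X ≥ 3) | Stated |
|---|---|---|---|
| 0.10 | 0.34868 + 0.38742 + 0.19371 = 0.9298 | 0.0702 | 0.07 |
| 0.15 | 0.19687 + 0.34743 + 0.27590 = 0.8202 | 0.1798 | 0.18 |
| 0.35 | 0.01346 + 0.07249 + 0.17565 = 0.2616 | 0.7384 | 0.74 |
| 0.40 | 0.00605 + 0.04031 + 0.12093 = 0.1673 | 0.8327 | 0.83 |

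All four reproduce. The formula depends only on p, the per-patient probability of the counted event. Renaming that event leaves every figure as it is.

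**2. The label against the event counted.** The two overlap without coinciding.

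- Fits the label and is counted: related, clinically significant non-hematologic toxicity of grade 3 or higher (outside the exceptions), and related grade 4 neutropenia, infection or infusion reaction.
- Fits the label but is not counted: grade 3 neutropenia, other grade 3 or higher hematologic toxicity, and the exempted grade 3 events.
- Counted but does not fit the label: clinical tumor lysis syndrome of grade 1 or 2 (Appendix D grades it from 1).

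The label takes no part in the decision. The trigger is applied by counting patients with the listed events.

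**3. The two definitions.**

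| | Synopsis | 13.4 |
|---|---|---|
| Window | AVO treatment | First triple cycle |
| Tumor lysis syndrome | Grade 4 or higher | Any clinical case |
| Stated exceptions | None | Asymptomatic laboratory findings; gastrointestinal symptoms that improve with supportive care |
| Rule attached | None | 3 or more of first 10 leads to DSMC consultation |

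The last row settles which definition applies. Only 13.4 attaches an action to the term, and its definition is complete.

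**4. Which text governs reporting.** Section 7 opens by saying that its own list of events, with the characteristics of the observed event, decides whether expedited reporting is needed. Section 7.8 repeats this for expedited reporting: listed events are reported only if they differ from the expected information. Section 7.9 sends sites to 7.4 for the criteria. Sections 7.3, 7.4 and 12.2 speak of expected or unexpected adverse events, and none of them uses the 13.4 term. A site following section 7 has no reason to take expectedness from the synopsis; if it did, it would over-report.

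**5. Other routes for the same events.** Serious adverse events go to the Overall PI whatever their expectedness (7.9). Tumor lysis syndrome is an event of special interest (7.2), due to both manufacturers within 15 calendar days (7.4). Grade 5 events are due in 1 business day under the 7.4 table, expected or not. Life-threatening toxicities go to the sponsor immediately (Appendix J). All events go on the routine toxicity forms (7.12).

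**6. Timing.** Section 2.4 reports twelve patients at the triple-therapy stage by 1/1/2019, against the ten the rule needs. Section 13.2 says cohort 1 has finished enrolling. The rule is a single count with no restart, so it is past or nearly so. Section 12.2 provides continuing DSMC review of toxicity for the whole protocol.

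**The case for a change.** The best case for a change is that nothing in the text says an unexpected toxicity and an unexpected adverse event are different things. The headings invite confusion: the synopsis defines unexpected toxicities, and 7.1 is titled with the direct opposite. Section 7.8 also mixes the vocabulary by judging adverse events against expected toxicity information, and it points to a list of protocol-specific exclusions that does not appear in 7.9 as supplied. The study was extended to community sites (2.4), where a single reading matters more. Section 13.4 does not say whether it covers cohort 2.

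The wording could indeed be cleaner, and that much stands. It does not lead to a wrong action. Section 7 says in terms that it decides expedited reporting, and 13.4 defines its own trigger. Silence on cohort 2 leaves little doubt, because a count of the first ten triple-therapy patients has no second start and 12.2 continues regardless.

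One could try to size the problem with the 40-50% rate of grade 3 or 4 neutropenia that section 7.1 gives for venetoclax. That rate does not measure it: neither definition counts grade 3 neutropenia, the grade 4 share is not given, and the figure is not a first-cycle rate.

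**Conclusion.** The inconsistencies are genuine, but they are clerical. The synopsis and 13.4 differ on window, tumor lysis threshold and exceptions, and the probability label in 13.4 names an overlapping but not identical event. The effect on any stated figure is zero: 0.07, 0.18, 0.74 and 0.83 are correct for whatever event p describes. No effect on the trigger, sample size, reporting or DSMC oversight is shown, and an analyst applying 13.4 as written would count the right events.

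This rests on two readings: that section 7 governs expedited reporting, as its opening and 7.8 say, and that the first-10 rule is a single look, as 13.4 words it. Whether a particular grade 4 event is expected under 7.3 depends on the prescribing information and brochure, which are not in the documents; the synopsis wording does not alter that. If the synopsis is next edited for another reason, the two lists and the label can be aligned then, with the content left to the sponsor. No change is called for now.
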